5.7 Concomitant Medications

Because of the potential for drug-drug interaction, the concurrent use of all other drugs, over-the-counter medications, or alternative therapies taken within 2 weeks prior to the start of the study must be documented on the case report form (CRF).

Patients receiving bisphosphonates or denosumab (RANK-L inhibitor) may continue on these agents as standard practice throughout the study.

Patients who enter the trial receiving prednisone or steroids must continue on the same dose they were receiving at the time of baseline assessment.

Permitted

- Pain Regimen Modification Guidelines:
 - An attempt to optimize a pain regimen should be made prior to subject enrollment. The investigator will optimize the subject's pain regimen under advisement/guidance of the 2.2014 NCCN Adult Cancer Pain guidelines. Opioid rotation, use of adjuvants, institution of a sustained release medication to minimize frequent prn dosing will be utilized depending on the severity of pain, degree of opioid tolerance and side effects under advisement/guidance of the NCCN guidelines. Use and optimization of short acting opioids followed, if needed, by adding an extended-release or long-acting formulation described in the protocol reflect NCCN guidelines. The patient will usually be allowed rescue doses of short-acting opioids of 10% to 20% of 24-h oral dose (mg) as needed as per the NCCN guidelines.
 - At the time of enrolment, the subjects pain regimen will be graded according to the WHO analgesia ladder:

Radium-223

MSKCC

PCCTC LOI: c13-124

IRB#: 14-098 A (5)

- Step 1- non-opioid analgesics
- Step 2- weak opioid (tramadol, codeine, hydrocodone)
- Step 3- strong opioid analgesic (morphine, oxycodone, fentanyl, oxymorphone, levorphanol, and methadone).
- NSAIDs, steroids and other adjuvant non-opioid analgesics can be included at each step of the analgesics ladder.
- Treatment with non-conventional therapies (e.g., herbs [with the exception of St. John's Wort], acupuncture) and vitamin/mineral supplements is acceptable provided that, in the opinion of the investigator, such treatment will not interfere with the trial endpoints.
- Subjects may receive standard of care for any underlying illness.

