- In the event of neutropenia, anemia, or thrombocytopenia, subjects may receive appropriate supportive care (e.g., transfusion, biologic response modifiers such as G-CSF or GM-CSF, prophylactic antibiotics, antifungals and/or antivirals, hematopoietic growth factors).
- Blood transfusions and erythropoietin are allowed during the study period but not within 4 weeks prior to first dose of study drug.
- If surgery is required during study drug treatment, the surgeon needs to be notified that the patient has been treated with a radioactive product and adequate precautions for radioactive protection should be applied during the surgical procedure. The patient should continue with study treatment if considered safe in the treating Investigator's opinion.

Concomitant treatments other than chemotherapy for prostate cancer are permissible, provided that they are started before the patient's pain assessments, and are not changed during the pain assessments. These agents will be recorded in the CRFs. These treatments may include, but are not necessarily limited to: Luteinizing-Hormone-Releasing hormone (LHRH) analogs, surgery, flutamide, bicalutamide, nilutamide, estramustine, ketoconazole, corticosteroids, estrogens, abiraterone, and enzalutamide.

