8. CRITERIA FOR OUTCOME ASSESSMENT/THERAPEUTIC RESPONSE

8.1 Primary endpoint

The primary endpoint of the study is a 30% decline in the BPI worst pain item from baseline to week 8, with a confirmed reduction at week 12 without an escalation of the subject's pain regimen from Step 1 to Step 2 or Step 2 to Step 3 of the WHO analgesic ladder.

The baseline BPI worst pain score average will be based on the worst pain scores completed by the patient in the 7 consecutive pretreatment days. A minimum of 4 days of pain scores must be completed by the patient in the 7 day window in order to calculate the average worst pain score.

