10. STATISTICAL CONSIDERATIONS

10.1 Study Endpoints

10.1.1 *Analysis of the primary endpoint*

The primary objective of this phase II study is to determine the effect of Radium-223 on pain improvement for patients with symptomatic metastatic castration-resistant disease. The primary endpoint of the study is a 30% decline in the BPI worst pain item from baseline to week 8, with a confirmed reduction at week 12 without an escalation of the subject's pain regimen from Step 1 to Step 2 or Step 2 to Step 3 of the WHO analgesic ladder. The baseline BPI worst pain score average will be based on the worst pain scores completed by the patient in the 7 consecutive pretreatment days. A minimum of 4 days of pain scores must be completed by the patient in the 7

day window in order to calculate the average worst pain score. We define this event as a response and propose declaring the treatment effective if the probability of a response in the population exceeds 0.20.

A maximum of 63 patients will be entered onto the study. A two-stage design that differentiates between response rates of 0.20 and 0.35 will be used to assess treatment efficacy. In the first stage of the study 27 patients will be enrolled. If at most 5 patients respond, accrual will be terminated. If at least 6 patients respond, an additional 36 patients will be entered onto the study. At the conclusion of this second stage, if at least 17/63 patients respond, the treatment will be declared effective. The probability of declaring the treatment effective is 0.10 when the response rate in the population is 0.20 and increases to 0.90 when the response rate is 0.35.

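### The steroid statements in Section 5.7 are not reconciled, and the primary endpoint can count pain relief after a newly started or increased steroid as a radium-223 response

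*Combined protocol and SAP*

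**What the plan says.** Section 5.7 (Concomitant Medications) speaks of steroids in three places, without cross-reference:

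- For patients already on them: "Patients who enter the trial receiving prednisone or steroids must continue on the same dose they were receiving at the time of baseline assessment".
- For concomitant prostate-cancer treatments other than chemotherapy, which are allowed "provided that they are started before the patient's pain assessments, and are not changed during the pain assessments". The examples include "estramustine, ketoconazole, corticosteroids, estrogens, abiraterone, and enzalutamide".
- In the list of permitted medication, under "Pain Regimen Modification Guidelines", after the definitions of the three WHO steps: "NSAIDs, steroids and other adjuvant non-opioid analgesics can be included at each step of the analgesics ladder". No start date or stable dose is required there.

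The primary endpoint is a 30% fall in BPI worst pain from baseline to week 8, confirmed at week 12. Its only analgesic condition is that this must occur "without an escalation of the subject's pain regimen from Step 1 to Step 2 or Step 2 to Step 3 of the WHO analgesic ladder" (Section 10.1.1; Sections 8.1 and 10.2.1 agree). Section 10.2.1 keeps every eligible, treated patient in the response analysis despite major deviations, and has no rule for a patient who starts or increases a steroid. The secondary analgesic comparison in Section 10.1.2 is in opiate equivalents.

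**The concern.** Two statements keep steroid exposure constant while pain is being measured. The third makes steroids neutral with respect to the ladder step and sets no such condition. A patient not on steroids at entry who is given one for pain is not clearly covered by either constancy statement, and the ladder bullet can be read as allowing it.

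The endpoint does not settle the matter. Because a steroid fits every step, starting one is never an escalation. If it is instead a protocol deviation, the patient still stays in the analysis and can still be scored a responder. The opiate-equivalent comparison would not show it, and there is no control arm in which the same relief would appear. To the extent that a new steroid relieves pain, it adds responders, and both the stage 1 decision and the final decision credit them to radium-223.

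**Working it through.** **Inputs from Section 10.1.1.** Stage 1 has 27 patients; accrual stops at 5 or fewer responders. Stage 2 adds 36. Success is at least 17 of 63. The rates to be distinguished are 0.20 and 0.35, with stated probabilities of declaring the treatment effective of 0.10 and 0.90.

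**The plan's own figures.** With X1 ~ Bin(27, p) and X2 ~ Bin(36, p),

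P(effective | p) = Σ over x = 6 to 27 of P(X1 = x) × P(X2 ≥ 17 − x).

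- p = 0.20: 0.0999, stated as 0.10.
- p = 0.35: 0.9019, stated as 0.90.

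Both reproduce, so the sample size and boundaries are not in question.

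**How few misattributed responses matter.** Assume that 0.20 is the response rate without steroid-driven responses. Let k be the average number of steroid-driven responders per 63 patients, so that p = 0.20 + k/63.

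| k | p | P(effective) |
|---|---|---|
| 0 | 0.2000 | 0.100 |
| 1 | 0.2159 | 0.167 |
| 2 | 0.2317 | 0.253 |
| 3 | 0.2476 | 0.354 |

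**What k implies.** Let f be the share of would-be non-responders who start or increase a steroid in time, and q the share of those who then meet the response criterion. Then p = 0.20 + 0.80 × f × q, and k = 63 × 0.80 × f × q = 50.4 × f × q. One extra responder needs f × q = 1/50.4 ≈ 0.02, for example 8% starting and a quarter of them gaining. Neither f nor q is in the documents, so the table below only shows the range.

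| f | q | p | P(effective) |
|---|---|---|---|
| 2% | 10% | 0.2016 | 0.106 |
| 5% | 10% | 0.204 | 0.115 |
| 5% | 25% | 0.21 | 0.140 |
| 10% | 25% | 0.22 | 0.187 |
| 10% | 50% | 0.24 | 0.304 |
| 20% | 50% | 0.28 | 0.575 |

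**Timing.** The 30% decline must be present at week 8. A steroid started after that assessment cannot create it, so f counts only starts and increases between baseline and the week 8 assessment. A later start could still help the week 12 confirmation.

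**The case against.** A reader might infer that Section 5.7 flatly contradicts itself. The text does not go that far. The ladder bullet speaks of including steroids, not adding them, and it follows the sentence on grading the regimen at enrolment. It can be read as a classification rule only. The three statements also differ in scope (patients on steroids at entry, corticosteroids as cancer treatment, composition of a ladder step), and all three can be obeyed together. Against this, the bullet stands under a heading about modifying the regimen, among permitted medication. The fair description is an ambiguity and a gap. The scoring problem does not depend on which reading is right.

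A reader might also infer that the stated 0.10 is wrong. It is not: it is stated for a population response rate of 0.20 on the endpoint as defined, and it reproduces. The documents do not say how 0.20 was chosen or whether it already allows for background changes in analgesia. If it does, some of the increase shown above is already built in.

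The size is also open. With few timely starts and little gain, the probability hardly moves (0.106 to 0.115); values above 0.5 need the most extreme inputs shown. Finally, the plan gives no reason for the constant-dose rule, so its purpose cannot be used as evidence.

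These objections stand. They limit how strongly the point can be put, but they do not supply the missing scoring rule.

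**Conclusion.** The point holds in a limited form. Section 5.7 leaves it unclear whether a steroid may be started for pain during the primary pain period, and its statements must be reconciled; the clinical choice is the sponsor's. Whichever reading applies, Sections 8.1, 10.1.1 and 10.2.1 allow a patient whose pain falls after a steroid is started or increased between baseline and week 8 to count as a radium-223 responder, and a single-arm design cannot reveal this.

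The defect is one of attribution, not a miscalculated error rate. Its size is conditional: if 0.20 excludes steroid-driven responses, one such responder per 63 on average takes the probability of a positive conclusion from 0.10 to about 0.17, and three take it to about 0.35. The documents give no frequency, so no single inflated error rate can be asserted. The change is worth making because the decision is sensitive to very few responses and the correction is cheap.

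**What to change.** 1. Reconcile the three steroid statements in Section 5.7 so that it is clear what applies to steroids used for any purpose during the primary pain period. The content of that rule is for the sponsor.
2. State in Sections 8.1, 10.1.1 and 10.2.1 that a patient with a corticosteroid newly started or dose-increased between the baseline week and week 12 is scored as a non-responder in the primary analysis. The window runs to week 12 so that it also covers the confirmation. This affects scoring only.
3. Report the response count under the present step-only wording as a sensitivity analysis.
4. Report starts of other adjuvant analgesics descriptively. Recoding them as well would go beyond the steroid question and replace the plan's step-based criterion.

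Cost: a few sentences. Section 5.2 already has concomitant medication monitored continuously, which matters because the analgesic diary covers only the run-in and the seven-day assessment periods. The response count may be slightly lower and will lose some patients who took a steroid for reasons other than pain. Scoring every corticosteroid start or increase, whatever the reason, means that the indication need not be recorded.

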6. THERAPEUTIC AGENT

6.1 Description of Treatments

Radium -223 (will be supplied as ready to use vial solutions for intravenous administration. The dose will be (50 kBq (0.00135 mCi) (55kBq (.0015 after NIST update) administered every 4 weeks for 6 doses.

Ra-223 will be administered as slow bolus injection over 1 minute.

Written instructions for handling and administration of Ra-223 will be given.

Ra-223 injection is a ready-to-use, sterile, free from endotoxins, clear and colorless aqueous solution of Radium-223 dichloride ($^{223}\text{RaCl}_2$) for intravenous administration. The volume per vial is 6 mL, corresponding to 6.6 MBq after implementation of the NIST with a

Radium-223

MSKCC

PCCTC LOI: c13-124

IRB#: 14-098 A (5)

radioactive concentration of 1,100 kBq/mL after implementation of the new NIST standard at the reference date. The product has a pre-calibration of 14 days.

Radium-223 is an alpha particle emitter with a physical half-life of 11.4 days. The product is isotonic and has a pH of 6.0 - 8.0. The radioactive concentration at the reference date is 1,100 kBq/mL after implementation of the NIST. The product has a pre-calibration of 14 days. When administered in a day other than the reference day, the volume should be corrected according to the physical decay table supplied with each shipment.

Radium Ra 223 dichloride is manufactured in Norway at a Bayer-contracted manufacturing site, IFE (Institute for Energy Technology), a specialized facility with a long history of manufacturing radiopharmaceuticals. The product is produced according to Good Manufacturing Practice (GMP).

Radium Ra 223 dichloride is then shipped to Cardinal Health for distribution in the United States. Cardinal Health prepares individualized patient ready doses based on patient weight and intended time of administration. The product is delivered in a glass vial, ready-to-use with a certified activity. Radium Ra 223 dichloride is shipped in a lead container with Type A radioactive packaging according to international transportation guidelines for radioactive materials. Patient ready doses to be utilized within study 14-098/c13-124 will be over-labeled with an "investigational use only" label at Cardinal prior to distribution to administering sites.

All study drugs will be labeled according to the requirements of local law and legislation. For all study drugs, a system of numbering in accordance with all requirements of GMP will be used, ensuring that each dose of study drug can be traced back to the respective bulkware of the ingredients.

6.2 Dosage Selected, Preparation, and Schedule of Administration

If the vials have been stored in a refrigerator, they should be left at room temperature for 1 hour prior to use. Ra-223 should not be diluted or mixed with any solutions.

The dose of Ra-223 is (50 kBq (0.00135 mCi) (55kBq (.0015 after NIST update) (unless, following discussions between the investigator(s) and sponsor, additional cohort(s) are added at intermediate Ra-223 dose levels between 25 and 55 kBq/kg). Radium Ra 223 dichloride will be administered as a bolus intravenous (IV) injection (up to 1 minute) at intervals of every 4 weeks for up to 6 cycles.

The dosage of Radium Ra 223 dichloride after implementation of the new 2015 NIST standard is 55kBq/kg body weight. The patient dose is calculated based on date of injection, a decay correction (DK) factor specific to number of days from reference date applied to correct for physical decay of radium-223, and patient weight. A table with DK values according to physical decay of the study medication will be provided with every shipment of Radium Ra 223 dichloride. Radium-223 is an alpha particle emitter with a physical $t^{1/2}$ of 11.4 days. After implementation of the NIST the radioactive concentration at the reference date is 1,100 kBq/mL.

The volume to be administered for dosing is calculated as follows:

$$\text{Volume to be} = \text{Body weight (kg)} \times \text{dose (55kBq/kg)}$$

Radium-223

MSKCC

PCCTC LOI: c13-124

IRB#: 14-098 A (5)

**administered after
implementation of the
new NIST standard (mL)**

b.w.]**DK factor × 1,100 kBq/mL**

Filling of the syringe should take place in a fume cupboard or safety bench in the Radiopharmacy/Nuclear Medicine department. Personnel should wear medical gloves and eye protection during syringe filling to prevent contamination of the radioactive solution to skin and eyes. The individual responsible for study drug preparation will draw the correct volume of study drug into a syringe. Data regarding activity and volume to be injected for the various patients should be recorded on the study drug administration CRF page.

To maintain traceability, there is one syringe label set per injection, with three identical removable stickers with a unique serial number, in addition to information of the radioactive material. One sticker with the serial number should be attached to the drug preparation page, the other on the syringe and the third to the CRF study drug administration page.

The syringe should be handed over to the individual who will perform the administration. There is no need for shielding from alpha particle radiation during preparation and administration of the patient doses. Alpha particles from radioactive decay of Radium-223 and progeny are easily stopped by the thickness of a sheet of a paper or the walls of a glass vial.

Aseptic technique should be used in the administration of Ra-223. The investigational drug will be administered as a slow bolus intravenous injection. After administration, the equipment used in connection with the preparation and administration of Ra-223, is to be treated as radioactive waste and should be disposed of in accordance with hospital procedure for the handling of radioactive material. Written information about Ra-223 and instruction about handling and administration of radioactive material will be given to study personnel.

Treatment will be administered on an outpatient basis.

6.2.1 Supply, storage requirements, and special handling

A dedicated person, who has the responsibility delegated from the Principal Investigator, will have the overall responsibility for handling and storage of study drug at the centre; i.e., that the vials with study drug are correctly received and recorded, handled and stored safely and properly, and used in accordance with this protocol. A deputy person should also be nominated. The study drug is a radiopharmaceutical and should be handled by individuals who are qualified by training and experience in the safe handling of radiopharmaceuticals.

The Ra-223 vials must be stored inside their lead container (of approximately 4 mm thickness) in a secure facility. The study drug should be used within the designated expiration date by manufacturer. The radioactivity of Ra-223 is measured by use of a radioisotope dose calibrator, calibrated for the isotope Radium-223. The radioactivity in the vial will be controlled at the hospital as part of the drug accountability, upon receipt of Ra-223 and after dispensing. The radioactivity of the syringe will be controlled before and after administration.

6.2.2 *Radiation protection*

In general, the administration of radioactive drugs involves a potential risk for third persons due to radiation from the patient and possible contamination by spilt urine, feces, blood, etc. An advantage of using Radium-223 is that once injected, both alpha and beta particles are stopped by the patient's tissue. Some gamma radiation is emitted from Radium-223 and its daughters. However, due to the low activity injected and attenuation in the patient's body mass, the gamma radiation outside the patient's body is minimal, and therefore the product can be administered on an outpatient basis. The patient and his caretakers will receive instructions in accordance to regulatory requirements regarding hygiene precautions after receiving the radioactive drug, to minimize the risk of contamination. The exposure rate constants from patients receiving Ra-223 or from handling vials or syringes with Ra-223 have been measured and are felt to not be of clinical concern.

6.3 **NIST Standardization**

The quantification of radium-223 radioactivity in Xofigo (radium-223 dichloride; BAY 88-8223) is based on the primary standardization performed by the US NIST. National Institute of Standards and Technology prepares the standard reference material (SRM) using an official dial setting (primary standardization) as published.¹⁶ The NIST SRM is used to calibrate the instruments in production and quality control for both the drug substance and drug product. Additionally, the NIST SRM is used to prepare the NIST traceable Ra-223 reference materials which are then sent to the end-users (e.g., nuclear medicine laboratory physicians or technicians) for dial-setting of their dose calibrators, to allow verification of the patient dose. In 2014, NIST performed a re-assessment of the primary standardization based on preliminary information suggesting a potential discrepancy of approximately 8-10% between the published NIST primary standardization¹⁶ and results obtained by other national metrology institutes (United Kingdom, Germany, Japan). After completion of the re-assessment, NIST reported their findings¹⁷ and had issued a revised NIST SRM in 2015. The discrepancy in the NIST standardization was determined to be -9.5% between activity values obtained using the old reference standard relative to the new primary standardization. Consequently the current numerical values need to be corrected by approx. + 10.5%.

The change in the numerical description of the patient's dose, product strength and labeled vial activity does not impact the safety or efficacy of Xofigo. The change in the NIST radium-223 standard has no impact on subjects; dose subjects are receiving, and will continue to receive.

Subjects will receive the same actual dose and volume that was studied in Study 15245 (BC1-06 dosimetry study) and is associated with the proven safety and efficacy of radium-223 dichloride, though the stated nominal radiation dose received has been updated to reflect the new standard.

7. **ADVERSE EVENTS**

7.1 **Definitions**

7.1.1 *Adverse Event (AE)*

Radium-223

MSKCC

PCCTC LOI: c13-124

IRB#: 14-098 A (5)

An adverse event is any untoward medical occurrence in a research patient during a clinical study or within 4 weeks post treatment, regardless of causality. This includes adverse clinical or laboratory findings, any adverse drug reaction (ADR), and an illness with onset during the study, or an exacerbation of preexisting illness or condition.

7.1.2 *Serious Adverse Event (SAE)*

The investigator must assess each event to determine if it meets the criteria for classification as an SAE or serious adverse drug reaction.

All SAEs that occur any time a patient is on study (i.e., as soon as the informed consent has been signed) or within 4 weeks of the last dose of Radium-223 must be recorded, regardless of the suspected relationship to the investigational agent. Any SAE occurring more than 4 weeks after the last dose of Radium-223 must be recorded if a causal relationship to the investigational agent is suspected.

An SAE/ADR as defined in the Code of Federal Regulations (21CFR312.32) is any event that:

- Results in death
- Is life-threatening
- Results in inpatient hospitalization or prolongation of existing hospitalization
- Results in persistent or significant disability or incapacity
- Results in congenital anomaly or birth defect
- Is medically significant in the opinion of the investigator

7.1.3 *Progression of malignancy*

Progression of a patient's malignancy should not be considered an AE, unless in the investigator's opinion, study treatment resulted in an exacerbation of the patient's condition. If disease progression results in death or hospitalization while on study or within 4 weeks of the last dose, progressive disease will be considered an SAE.

7.1.4 *Life-threatening events*

A life-threatening event is any AE that places the patient at immediate risk of death from the reaction as it occurs. It is not a reaction that, had it occurred in a more severe form, might have caused death.

7.1.5 *Hospitalization or prolongation of hospitalization*

Hospitalization encompasses any inpatient admission (even for less than 24 hours) resulting from a precipitating, treatment-emergent adverse event. For chronic or long-term patients, inpatient admission also includes transfer within the hospital to an acute or intensive care inpatient unit. Hospitalizations for administrative reasons or a non-worsening preexisting condition should not be considered AEs (e.g., admission for workup of a persistent pretreatment laboratory abnormality, yearly physical exam, protocol-specified admission, elective surgery). Preplanned treatments or surgical procedures should be noted in the baseline documentation. Hospitalization because of an unplanned event will be deemed an SAE.

Radium-223

MSKCC

PCCTC LOI: c13-124

IRB#: 14-098 A (5)

Prolongation of hospitalization is any extension of an inpatient hospitalization beyond the stay anticipated or required for the original reason for admission.

7.1.6 *Significant disability*

Disability is a substantial disruption of the patient's ability to conduct normal life functions.

7.1.7 *Congenital anomaly*

If the female partner of a male patient becomes pregnant during the course of the study, the treating physician must be notified immediately. All confirmed pregnancies must be immediately reported to Bayer and PCCTC and recorded in PCCTC Caisis EDC. All pregnancies will be followed until resolution (i.e., voluntary or spontaneous termination or birth) and assessed for congenital anomalies and birth defects. Patients receiving Ra-223 will be instructed to avoid conception for at least 6 month after last administration of Ra-223.

7.1.8 *Medical significance*

An event that is not fatal or life-threatening and that does not necessitate hospitalization may be considered serious if, in the opinion of the investigator, it jeopardizes the patient's status and might lead to medical or surgical intervention to prevent any of the above outcomes. Such medically significant events could include allergic bronchospasm requiring intensive treatment in the emergency room or at home, blood dyscrasias that do not result in inpatient hospitalization, or the development of drug dependency or abuse.

The NCI CTCAE v4.0 handbook will be used for adverse event descriptions and grading.

Follow-up of adverse events should continue until the event and any sequelae resolve or stabilize at a level acceptable to the investigator and the study site/sponsor or medical monitor.

Events that are **not** considered serious adverse events include:

- Routine treatment or monitoring of the studied indication, not associated with any deterioration in condition, or for elective procedures
- Elective or pre-planned treatment for a pre-existing condition that did not worsen
- Emergency outpatient treatment for an event not fulfilling the serious criteria outlined above and not resulting in inpatient admission
- Respite care

